5.4.5.1 PAH-specific therapies

PAH-specific therapies will be identified by a search of WOHDD PTs and ingredients as shown in [Table 5](#). Specific summaries will be prepared:

Ongoing PAH-specific therapies at baseline will be summarized. PAH-specific therapies that are newly started, dose changed, or stopped during any study period will be listed in a separate listing.

PAH-specific therapies will be displayed in a listing with the respective study period flagged.

Table 5 PAH-specific therapies

Category	Subcategory	Ingredient names
Antihypertensives for pulmonary arterial hypertension	ERAs	Ambrisentan, Bosentan, Macitentan
	PDE-5 inhibitors	Sildenafil, Tadalafil, Vardenafil
	sGC stimulator	Riociguat
Prostanoids		Epoprostenol, Treprostil, Iloprost,
Uptravi		Selexipag

Categories are identified by searching the coded WHODRUG preferred terms for occurrence of any of the ingredient names, e.g., 'Sildenafil' and 'Sildenafil Citrate' will both be assigned to PDE-5 inhibitors.

ERA = endothelin receptor antagonist; PAH = pulmonary arterial hypertension; PDE-5 = phosphodiesterase type-5; sGC = soluble guanylate cyclase.

5.4.5.2 Auxiliary medications

Oral Uptravi is collected as a mandatory background drug in the previous and concomitant medication page. Dose changes will be listed with PAH-specific therapies.

5.5 Study treatment exposure and compliance

i.v. selexipag is considered the only study treatment for this study.

5.5.1 Exposure

5.5.1.1 Exposure to i.v. selexipag

The number and percentage of subjects being exposed to one, two, or three infusions of i.v. selexipag will be summarized.

The planned i.v. selexipag dose [μg] for each infusion will be summarized as a continuous variable as well as a categorical variable using categories from [Table 6](#). The actual i.v. selexipag dose will be summarized separately. Total actual time of infusion in minutes will be summarized for each of the three infusions as well.

The summary will be conducted for each of the three infusions separately.

The dosage administration records will be listed together with the reasons for dose change and dosage end as recorded in the eCRF.

5.5.1.2 Exposure to Uptravi prior and post- i.v. selexipag

The actual Uptravi dose [μg] will be collected and summarized by dose category for the four time points surrounding the i.v. administration of selexipag, i.e., evening dose before Visit 2 Day 1, morning and evening dose at Visit 2 Day 1 and evening dose at Visit 2 Day 3.

The Uptravi dosage records will be listed.

5.5.1.3 Shift in selexipag dose between oral and i.v. treatment

The shift from actual oral to i.v. and back to oral doses will be analyzed graphically in a series plot showing the individual dose in [μg] for each dose administration time point during Day 1 through Day 3 of Visit 2.

The i.v. selexipag doses administered will be converted to their oral dose equivalents [see [Table 6](#)] to facilitate the review.

5.5.1.4 Study treatment adjustments or interruptions, end of infusion status

Incidence of and reasons for i.v. administration interruption as well as the end of infusion status (irrespective of whether study treatment was completed as per protocol or not) will be summarized for each of three infusions.

5.5.2 Compliance with study treatment

Compliance with i.v. selexipag treatment is defined as the percentage of the actual dose infused compared with the planned dose to be infused, for each infusion and overall.

The planned dose to be infused will be determined from [Table 6](#) below and based on the subjects' stable Uptravi dose taken from the Visit 2 Day 1 evening dose.

Table 6 Correspondence of i.v. selexipag dose compared to Uptravi oral doses

Uptravi oral dose (μg)	Corresponding i.v. selexipag dose (μg)
200	225
400	450
600	675
800	900
1000	1125
1200	1350
1400	1575
1600	1800

The actual infused dose will be computed by computing the product of the infusion rate (mL/h) with the concentration of infusion solution (μg/mL) as recorded in the eCRF and the elapsed time between start and end time (h) for each infusion to obtain the amount of i.v. selexipag infused.

Missed infusions will be entered with 0 μg actual infusion into the compliance analysis.

The planned dose, actual dose, and resulting compliance will be listed. Compliance will be summarized descriptively for each period and overall.

6 EFFICACY VARIABLES AND ANALYSES

Not applicable in this study.

7 SAFETY VARIABLES

7.1 Overview of safety analyses including subgroup analyses

7.1.1 Overview of safety and tolerability endpoints

Safety endpoints in this study comprise the incidence of AEs and serious AEs (SAEs), discontinuations due to AEs, change and newly occurring abnormalities in vital signs, ECG and clinical laboratory values, as well as change in WHO FC and body weight.

The analysis of safety endpoints in different analysis periods [see [Table 2](#)] is summarized in [Table 7](#) below.

Table 7 Overview of safety and tolerability endpoints and populations in planned analysis periods

Endpoint	SCR (Scr)	1 (S)	2 (ivS)	3&FU (ivS)	1&2 (S)	2&3&FU (ivS)	1&2&3&FU (S, ivS)
Main safety and tolerability endpoints							
AEs and SAEs	✓	✓	✓	✓	✓	✓	✓
Prostacyclin-associated AEs ¹ leading to discontinuation of study drug			✓				
Prostacyclin-associated AEs ¹		✓	✓	✓	✓	✓	✓
Injection site reaction AEs ¹			✓				
PAH related AEs ¹		✓	✓	✓	✓	✓	✓
Other safety and tolerability endpoints							
AEs leading to discontinuation of study drug				✓			
AEs related to study drug as judged by the investigator			✓	✓		✓	✓
Deaths during study							✓
ECG abnormalities, QT prolongation		✓	✓	✓	✓	✓	✓
Marked laboratory abnormalities		✓	✓	✓		✓	✓
Marked blood pressure abnormalities		✓	✓	✓		✓	✓
Change from baseline in WHO functional class ²		✓	✓	✓	✓	✓	✓

Periods connected by an ampersand will be analyzed combined.

All analyses will be run on the S, if S and ivS are identical.

¹ As defined by MedDRA search terms ² By visit analyses

(S) = Safety analysis Set, (ivS) = i.v. Safety analysis set, (Scr) = Screened subject set; AE = adverse event; ECG = electrocardiograph; FU = Safety Follow Up; MedDRA = Medical Dictionary for Regulatory Activities; PAH = pulmonary arterial hypertension; SAE = serious adverse event; SCR = Screening period, WHO = World Health Organization.

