5.1.10 Premature discontinuation of study treatment

A subject is considered as having prematurely discontinued study treatment if the third i.v. selexipag infusion was not initiated.

The decision to prematurely discontinue i.v. selexipag treatment may be made by the subject, the investigator or Actelion personnel. The main reason and whether discontinuation of i.v. selexipag treatment is the decision of the subject (e.g., tolerability- or efficacy-related), the investigator (e.g., due to pre-specified i.v. selexipag treatment discontinuation criteria, an AE or lack of efficacy), or Actelion (e.g., study terminated) must be documented in the CRF.

A subject has the right to discontinue i.v. selexipag treatment at any time, without any justification, by withdrawal from study treatment only or by withdrawal from any further participation in the study (i.e., premature withdrawal from the study [see Section [8.2](#)]). Although a subject is not obliged to provide his/her reason for prematurely withdrawing from the treatment or the study, it is recommended that the investigator makes a reasonable effort to ascertain the reason(s), while fully respecting the subject's rights.

The investigator must discontinue i.v. selexipag treatment for a given subject if, he/she believes that continued administration would be contrary to the best interests of the subject.

Study-specific criteria for discontinuation of i.v. selexipag treatment are described in Section [5.1.11](#).

A subject who prematurely discontinues i.v. selexipag treatment is to be discontinued from the study. For safety reasons, it is recommended to perform the assessments of Visit 3. The EOS telephone call (Visit 4) must be performed, provided that the subject's consent for this limited participation in the study has not been withdrawn. The assessments that are to be performed at each visit are described in [Table 2](#).

A subject who prematurely discontinues i.v. selexipag treatment and withdraws consent to participate in any further study assessments is considered as withdrawn from the study. Subjects who die or are lost to follow-up are also considered as withdrawn from the study. Withdrawal from the study and follow-up medical care of subjects withdrawn from the study is described in Sections [8.2](#) and [8.4](#), respectively.

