6.2.2 Main safety and tolerability endpoints

The main safety and tolerability endpoints will be analyzed over Period 1, Period 2, and Period 3 and follow-up period combined.

- Discontinuations due to prostacyclin-associated AEs.
- AEs and SAEs.
- Prostacyclin-associated AEs.
- AEs related to injection site reactions.
- PAH-related AEs.

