6.2.3 Other safety and tolerability endpoints

The other safety and tolerability endpoints will be analyzed:

- For each study period separately: Period 1; Period 2; Period 3 and follow-up period combined.
- For Period 1 and Period 2 combined.
- For Period 2 and Period 3 combined.

The following endpoints will be analyzed:

- Discontinuations due to prostacyclin-associated AEs.
- Discontinuations due to any AEs.
- AEs and SAEs.
- Prostacyclin-associated AEs.
- PAH-related AEs.

- Change from baseline in vital signs (SBP, diastolic blood pressure [DBP], and pulse rate) and body weight.
- ECG abnormalities.
- Marked laboratory abnormalities (MLAs).
- Change from baseline in WHO FC.

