10.1.6 Usage of the analysis sets

Subject disposition is described for the Screened Analysis Set. Demographics and baseline characteristics will be reported on the SAF. Safety analyses will be carried out on the SAF and on the i.v. Safety Set. PK analyses will be carried out on the PKS. Subject listings are based on the SAF or Screened Analysis Set as applicable. The following table describes the use of the analysis sets.

Table 4 Reporting periods and corresponding analysis sets.

Reporting period(s)*	Variables	Analysis set
Period 1	Safety and tolerability	SAF
Period 2	Safety and tolerability	i.v. Safety Set
Period 3	Safety and tolerability	i.v. Safety Set
Period 1 and 2	Safety and tolerability	SAF
Period 2 and 3	Safety and tolerability	i.v. Safety Set
Period 1 and 2 and 3	Safety and tolerability	SAF
Period 1 and 2	Pharmacokinetic	SAF, PKS

Follow-up period will be reported together with Period 3.

* If a subject does not take at least one dose of selexipag i.v. they will not be considered as having entered Period 2 (or 3).

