10.3.4 Analysis of the safety variable(s)

The study comprises 3 main periods for analysis, Period 1 (Uptravi, pre-treatment), Period 2 (i.v. selexipag; treatment period) and Period 3 (Uptravi; post-treatment).

Tolerability and safety analyses will be carried out descriptively on the SAF and the i.v. Safety Set. AEs that occur prior to first intake of Uptravi on Day 1 as a result of study-mandated procedures will be analyzed descriptively in the Screened Analysis Set. All AEs and SAEs will be coded using MedDRA.

The number and percentage of subjects experiencing AEs by period [as per [Table 4](#)] will be tabulated by MedDRA System Organ Class (SOC) and individual Preferred Term (PT) within each of the SOCs, in descending order of incidence of SOC, alphabetical order of PT, PT descending order of incidence and alphabetical order of PT for each period separately. AEs and SAEs will be tabulated, for the SAF and i.v. Safety Set overall across periods as well as by study period. The same summary applies to SAEs, AEs leading to premature discontinuation of study treatment and death. Furthermore, AEs and SAEs will be tabulated by severity and relationship to i.v. selexipag.

The proportion of discontinuations due to prostacyclin-associated AEs and AEs leading to discontinuation will be tabulated for the SAF and i.v. Safety Set (as well as all other discontinuations, irrespective of reason). Due to the small sample size, estimates of the proportion will be provided with a conservative 95% Clopper-Pearson CI based on exact methods.

Safety endpoints will be listed and tabulated in the SAF and i.v. Safety Set, overall and by study period [see [Table 4](#) for details]. Treatment exposure will be summarized. Selexipag dose (oral and i.v.) will be summarized by visit, number of subjects and percentage. Shift tables between oral and i.v. dose will also be provided.

ECG abnormalities and laboratory variables will be descriptively summarized, both longitudinally across the study periods as well as separately per period. Death will be summarized by cause, by period, and overall.

All laboratory test assessments will be listed by subject, for all subjects in the SAF and will be tabulated on the SAF and i.v. Safety Set. Descriptive summary statistics by visit will be provided for observed values and absolute changes from baseline.

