	
- i.v. Safety Set comprises all subjects who received at least one dose of i.v. study treatment.- Safety Set (SAF) includes all enrolled (included in the study on Day 1) subjects who receive at least one dose of selexipag (oral or i.v.).- Pharmacokinetic Analysis Set (PKS) comprises all subjects included in the SAF who received the 3 doses of i.v. study treatment and who complied with the protocol sufficiently and did not deviate from the protocol in a way that might affect the PK outcome of the study. 
The study comprises 3 main periods for analysis: Period 1, Period 2, and Period 3 and follow-up. AEs and SAEs will be tabulated, for the Safety Set and i.v. Safety Set, overall across periods as well as by study period. The proportion of discontinuations due to prostacyclin-associated AEs will be tabulated for the i.v. Safety Set and the SAF to address the primary objective. Due to the sample size, the proportion will be provided with a conservative 95% Clopper-Pearson confidence interval based on exact methods.
 
All secondary safety endpoints will be listed and tabulated in Safety Set and i.v. Safety Set.
 
Exposure will be summarized.
 
ECG abnormalities and laboratory variables will be descriptively summarized, both longitudinally across the study periods as well as separately per period. Death will be summarized by cause, by period, and overall.
 
The proportion of patients in each WHO FC (I, II, III and IV) will be tabulated at baseline and post-baseline, as well as the change in WHO FC at all assessed time points. Also the absence of worsening in WHO FC will be tabulated (i.e., patients that are either stable or improve).

--	---

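### SAP Table 7, as it reads, confines the main discontinuation endpoint to Period 2, while the protocol asks for all periods combined and by period

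*SAP*

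**What the plan says.** **Period.** Protocol 6.2.2, whose list begins with this endpoint, states: "The main safety and tolerability endpoints will be analyzed over Period 1, Period 2, and Period 3 and follow-up period combined". Protocol 6.2.3 repeats the endpoint, to be shown "For each study period separately: Period 1; Period 2; Period 3 and follow-up period combined", and also for Periods 1 and 2 combined and Periods 2 and 3 combined.

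**Analysis set.** Protocol 10.3.4 states: "The proportion of discontinuations due to prostacyclin-associated AEs and AEs leading to discontinuation will be tabulated for the SAF and i.v. Safety Set". The synopsis, reproduced in SAP Appendix A, gives the reason: "The proportion of discontinuations due to prostacyclin-associated AEs will be tabulated for the i.v. Safety Set and the SAF to address the primary objective". Protocol Table 4 assigns the reporting period "Period 1 and 2 and 3" to the SAF.

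**SAP Table 7.** The row for prostacyclin-associated AEs "leading to discontinuation of study drug" has one tick, which reads as the Period 2 (ivS) column. A footnote adds: "All analyses will be run on the S, if S and ivS are identical". SAP 7.2.2 prepares the AE summary tables for the periods in Table 7 and assigns each AE to a period by its start date and time.

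**Elsewhere in the SAP.** Table 4 plans AE analyses for all periods plus follow-up on both SAF and ivSAF. Section 12.7.3 lists this output (AE_PCDC_PT) on both sets; its title names no period, although the two other outputs in that section are by period. Section 12.7.7 lists the table for any AE leading to discontinuation on ivSAF only. Section 7.2.1.4 counts an AE only if the action recorded for study treatment is withdrawal of the drug, and 5.5 makes i.v. selexipag the only study treatment. Section 11.1 records no changes from the protocol.

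**The concern.** The synopsis ties this proportion to the primary objective. A programmer following 7.2.2 and Table 7 would produce a Period 2 table. One following the protocol would produce an all-period table with period breakdowns. The 12.7.3 title does not settle the choice.

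The two tables can have different numerators because period is decided by AE onset, not by when the drug is stopped. Period 1 runs from the Day 1 morning oral dose to just before the first infusion on Day 2. Suppose a headache starts on the evening of Day 1, persists, and leads to i.v. selexipag being stopped after the first infusion. It is a Period 1 AE, so a Period 2 table would not count it. Any such omission lowers the reported rate of a tolerability measure.

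**Working it through.** **1. The plan's own precision figures.** Inputs from SAP 2.5 and protocol 10.5: about 20 enrolled, 18 in the i.v. set, 95% upper limits not above 35% (i.v. set) and 32% (SAF). The Clopper-Pearson upper limit for x events in n subjects is the 0.975 quantile of Beta(x + 1, n − x).

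- 2/18 = 11.1%, upper limit 34.7%, which fits 35%.
- 2/20 = 10.0%, upper limit 31.7%, which fits 32%.

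Both figures are reproduced with two events. SAP 2.5 therefore presupposes a SAF analysis of this endpoint. It also speaks of discontinuations over the whole study.

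**2. The specifications side by side.**

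| Source | Period | Set |
|---|---|---|
| Protocol 6.2.2 | 1, 2, 3 and follow-up combined | – |
| Protocol 6.2.3 | each period; 1 and 2; 2 and 3 | – |
| Protocol 10.3.4, synopsis | – | SAF and i.v. set |
| SAP Table 7 | Period 2, as read | ivS (S if the sets are identical) |
| SAP Table 4 (AEs, all periods plus follow-up) | combined | SAF and ivSAF |
| SAP 12.7.3 | none named | SAF and ivSAF |

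The set is covered outside Table 7. The period is not.

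**3. Effect of one Period 1 AE that leads to i.v. withdrawal.** The count is an assumption. For x = 0 the upper limit is 1 − 0.025^(1/n). For x = 1 it is the p that solves (1 − p)^n + n·p·(1 − p)^(n−1) = 0.025.

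- All 20 infused, sets identical. Table 7: 0/20, upper limit 1 − 0.025^(1/20) = 16.8%. Protocol: 1/20 = 5.0%, upper limit 24.9%. The difference in upper limits is 24.9 − 16.8 = 8.1 points.
- 18 infused, i.v. set. Table 7: 0/18, upper limit 1 − 0.025^(1/18) = 18.5%. Protocol: 1/18 = 5.6%, upper limit 27.3%. The difference is 27.3 − 18.5 = 8.8 points.

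The footnote on identical sets changes the set in the first case but restores no period, so the event is still missed.

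**4. A subject who stops before the first infusion.** This is a separate matter. Under 7.2.1.4 the AE must carry a withdrawal of i.v. selexipag, and a subject never infused may have no such record. Such a subject could therefore go uncounted on the SAF even with the all-period column ticked.

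**5. Which added columns can hold events.** Protocol 5.1.10 defines the event: "A subject is considered as having prematurely discontinued study treatment if the third i.v. selexipag infusion was not initiated". An AE starting in Period 3 or follow-up cannot cause that, so a Period 3 and follow-up column would be empty. Period 1, Period 2, Periods 1 and 2, and Periods 2 and 3 with follow-up can be non-empty.

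**The case against.** **The tick may be misread.** The column is taken from a text rendering of Table 7, where a merged cell would not show. The neighbouring row, AEs leading to discontinuation, reads as Period 3 and follow-up only, which step 5 shows to be impossible. This stands as a reason to check the original. Against it, the other single-tick rows land sensibly: deaths under all periods, injection site reactions under Period 2. A reader might count the Period 3 and follow-up tick as a second error; it may only be a fault of the rendering.

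**The sets are already planned.** This stands. A reader of Table 7 alone might infer that the SAF analysis was dropped; SAP Table 4, 12.7.3 and 2.5 show otherwise. The plain set mismatch is 12.7.7, which departs from protocol 10.3.4 wherever the tick belongs.

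**Section 12.7.3 does not contradict Table 7 on period.** This also stands. Its shell, T_AE_PT, has labels for six period groupings but is shared by many outputs. The section is silent rather than opposed.

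**Larger contrasts are not due to Table 7 alone.** One might set 0/18 (18.5%) against 2/20 (31.7%) by assuming two pre-infusion stops. That gap depends also on the withdrawal definition in 7.2.1.4, so it cannot be charged to the tick.

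**Few cases, and visible ones.** i.v. selexipag is given only in Period 2, subjects have been on an unchanged oral dose for at least 28 days, and Period 1 lasts one day. A wholly missing AE onset is imputed to the first infusion (SAP 10.5) and so falls in Period 2. Disposition and discontinuation tables and the AE listing would still show individual cases. This limits the weight of the point but does not remove the mismatch.

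**Conclusion.** The point holds for the period. Table 7, as it reads, plans the endpoint for Period 2 only; the protocol requires all periods combined and by period; and the SAP declares no change. The set requirement for this endpoint is met elsewhere in the SAP.

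The size is small and may be zero. One Period 1 AE leading to i.v. withdrawal would move the estimate from 0% to 5.0% or 5.6%, and the upper limit by about 8 to 9 points. The documents do not say how likely such an event is. The conclusion assumes that the tick belongs to Period 2 in the original layout and that programming follows 7.2.2. A tick under all periods would leave only the by-period displays missing from Table 7; a merged cell could weaken the point further. No hypothesis is tested and cases remain traceable, so the severity is minor to should-fix.

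**What to change.** 1. Check the row's tick in the original layout. Check the tick for AEs leading to discontinuation at the same time, and change that one only if the original is wrong.
2. In Table 7, tick the column for all periods plus follow-up (S, ivS) as the main display for this row. Add the protocol 6.2.3 columns that can be non-empty.
3. Name the period in the title of the 12.7.3 output, and add the SAF to 12.7.7 to match protocol 10.3.4.
4. In 7.2.1.4, state that a subject who stops before the first infusion because of a prostacyclin-associated AE counts on the SAF. Identify such a subject from the AE record together with the study-discontinuation reason; the discontinuation table T_PWDS alone carries no AE term.
5. If the Period 2 restriction is intended, declare and justify it in SAP 11.1 instead.

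The cost is SAP wording and at most a rerun of the two discontinuation tables. Shell T_AE_PT already has the period labels, and sample size and data collection do not change.
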